8.2.5.4 Regulatory Reporting Requirements for Serious Adverse Events
If subject is permanently withdrawn from protocol-required therapies because of a
serious adverse event, this information must be submitted to Amgen.

Date: 21 April 2022 Page 62 of 108

Prompt notification by the investigator to the sponsor of **serious adverse events** is essential so that legal obligations and ethical responsibilities towards the safety of subjects and the safety of a study treatment under clinical investigation are met.

The sponsor has a legal responsibility to notify both the local regulatory authority and other regulatory agencies about the safety of a study treatment under clinical investigation. The sponsor will comply with country-specific regulatory requirements relating to safety reporting to the regulatory authority, IRBs/IECs, and investigators.

Individual safety reports must be prepared for suspected unexpected serious adverse reactions according to local regulatory requirements and sponsor policy and forwarded to investigators as necessary.

An investigator who receives an individual safety report describing a **serious adverse event** or other specific safety information (eg, summary or listing of **serious adverse events**) from the sponsor will file it along with the Investigator's Brochure and will notify the IRB/IEC, if appropriate according to local requirements.

8.2.5.5 Safety Monitoring Plan

Subject safety will be routinely monitored as defined in Amgen's safety surveillance and signal management processes.

8.2.5.6 Pregnancy and Lactation

Details of all pregnancies and/or lactation in female subjects and female partners of male subjects will be collected after the start of study treatment and through an additional 48 hours after the last dose of protocol-required therapies.

If a pregnancy is reported, the investigator is to inform Amgen within 24 hours of learning of the pregnancy and/or lactation and is to follow the procedures outlined in Section 11.5. Amgen Global Patient Safety will follow-up with the investigator regarding additional information that may be requested.

Abnormal pregnancy outcomes (eg, spontaneous abortion, fetal death, stillbirth, congenital anomalies, ectopic pregnancy) are considered SAEs.

Further details regarding pregnancy and lactation are provided in Section 11.5.

8.2.5.7 Adverse Device Effects

In order to fulfill regulatory reporting obligations worldwide, the investigator is responsible for the detection and documentation of any adverse device effects that occur during the study with such devices.

Date: 21 April 2022 Page 63 of 108

Further details regarding adverse device effects can be found in Section 11.4.

An adverse device effect is any **adverse event** related to the use of a combination product (**definition of combination product is provided in Section 11.4**) or medical device. Adverse device effects include, but are not limited to, adverse events resulting from insufficient or inadequate instructions for use, adverse events resulting from any malfunction of the device, or adverse events resulting from use error or from intentional misuse of the device.

All adverse device effects are to be reported as **adverse events** following the same reporting periods and procedures.

The CH will provide the monitoring devices and related training to the sites. The sites will then provide the monitoring devices and the training to the subjects. A 24/7 help hotline is available for any CWHMS related issues. The CH hotline will be trained on how to report product related device incidents (with or without associated AE) and product complaints to the site as per the approved protocol design. All monitoring device related complaints/AEs will be reported in the Clinical Trial Database and relayed to the CH for reporting since all the defined monitoring devices are part of their 510k clearance.

Product complaints are described in Section 6.1.4.

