Study Day within Cycle	D- 21 to D-1	D-14	D- 3 to				D29 (± 7 d ays)	D1	D2	D29 (± 3 days)	End of C2 Clinical Assessment (D29)	(C3, optional cycle)	(C4, optional cycle)	(30 days + 3 days post last dose blinatumomab)	
Clinical Chemistry (contin	nued)														
Serum and/or Urine pregnancy test (females of childbearing potential only)															Additional on-treatment pregnancy testing may be performed at the investigator's discretion if there is suspicion that a female subject is pregnant or per local laws and regulations. A highly sensitive (urine or serum) pregnancy test should be completed at screening and within 7 days of initiation of investigational product for females of childbearing potential.
Urinalysis	Χ														
Bone marrow MRD							Х								According to institution practice.
DIGITAL HEALTH Eligibility for home monitoring and wearables		Х													
CWHMS kits delivered to site	Х														Monitoring device kits will be sent to site at site initiation. Each kit will have duplicate devices and an oral thermometer to be used as needed.
Subject home monitoring device training.		Х													
Caregiver eligibility and device monitoring training		Х													

Page 4 of 7

Date: 21 April 2022 Page 24 of 108

Table 1-2. Schedule of Activities

PROCEDURE		reenir 21 day	•	су	cle 1	(C1)				cycle 2 (C2	2)	cycle 3 (C3)	cycle 4 (C4)	EOS	Notes
Study Day within Cycle	D- 21 to D-1	D-14 to D-7	3 to	D2	D3	D4	D29 (± 7 d ays)	D1	D2	D3	D29 (± 3 days)	End of C2 Clinical Assessment (D29)	(C3, optional cycle)	(C4, optional cycle)	(30 days + 3 days post last dose blinatumomab)	
DIGITAL HEALTH																
PI/Site device monitoring training		x														Site training will be completed at initiation and during the screening period for the first subject is enrolled. Training may be required for first subject only. Any subsequent training will be requested ad hoc
Subject home trial period of CWHMS assessed for 24-48 hours to determine eligibility.		X														Recommend to be completed at least 1 week prior to start of treatment (during screening, subjects should test wearing of devices and data transmittal for a minimum of 24 hours). During this screening device testing period, the study doctor will not be monitoring the device. The subject or caregiver must immediately contact the study doctor directly if the subject is feeling unwell during the screening period.

Page 5 of 7

Date: 21 April 2022 Page 25 of 108

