PROTOCOL-SPECIFIE	D PR	OCED	URES	3													
Blinatumomab treatment	21 days of sig Continuously throughout the 28-day infusion period for each cycle Subjects will sinfusion in the											Enrollment should occur within 21 days of signing ICF. Subjects will spend the first 5 hours of infusion in the outpatient department for C1D1 and 1-2 hours for C2D1.					
EORTC QLQ-C30	x			(X)					x								(X): First EORTC QLQC30 can be completed at screening or C1D1 (predose). EORTC QLQC30 will also be done at C2D1
Concomitant medications			ı				←	Contin	uous	ly fro	m S	creening th	rough end of stu	ıdy →		1	
Adverse events								← F	Repor	t fron	n cy	cle 1 day 1	treatment throu	gh end of st	udy →		
Serious adverse events						← 1	Repo	ort from	Signi	ing of	f Info	ormed Cons	ent through en	d of study→	•		
Adverse device effects							\leftarrow	Contin	uous	ly fro	m S	creening the	rough end of stu	ıdy →			
Survival Status														(X)	(X)	Х	In case of premature treatment discontinuation, subjects will be required to complete the end of study visit approximately 30 (+ 3) days after the last dose of blinatumomab. Only safety and survival data to be collected. (X): To be collected on day 1 to determine eligibility to receive optional cycles

Page 7 of 7

Date: 21 April 2022 Page 27 of 108

ALL = acute lymphoblastic leukemia; ALP = alkaline phosphatase; ALT = alanine aminotransferase; aPTT = activated partial thromboplastin time; AST = aspartate aminotransferase; **BM** = **bone marrow**; BP = blood pressure; BSA = body surface area; BUN = blood urea nitrogen; C = cycle; CBC = complete blood count; CR = complete remission; CSF = cerebrospinal fluid; CWHMS = Current Wearable Health Monitoring System; D = day; ECG = electrocardiogram; ECOG PS = Eastern Cooperative Oncology Group Performance Status; **EORTC QLQ-C30 = European Organization for Research and Treatment of Cancer Quality of Life Questionnaire**; EOS = end of study; HCP = healthcare provider; ICF = informed consent form; INR = international normalized ratio; LDH = lactate dehydrogenase; MDMP = mandatory device monitoring period; MRD = minimal/measurable residual disease; PI = principal investigator; PT = prothrombin time; PRO = Patient Reported Outcomes; ULN = upper limit of normal

Date: 21 April 2022 Page 28 of 108

2. Introduction

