8.2.1.3 Medical History/Current Medical Conditions

The Investigator or designee will collect a complete medical and surgical history that started 3 years prior to screening through time of signing of informed consent. In addition, any non-serious Adverse Event that is observed between the signing of the Informed Consent Form to enrolment/pre-dose cycle 1 day 1 should be captured as Medical History. Medical history will include information on the subject's concurrent medical conditions. Record all findings on the medical history CRF. In addition to the medical history above, all history related to the subject's diagnosis of MRD positivity will be recorded. The current toxicity grade will be collected for each condition that has not resolved.

Date: 21 April 2022 Page 56 of 108

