8.2.5.1 Time Period and Frequency for Collecting and Reporting Safety Event Information

8.2.5.1.1 Adverse Events

The **adverse event** grading scale to be used for this study will be the CTCAE v5 and is described in Section 11.4.

The investigator is responsible for ensuring that all **adverse events** observed by the investigator or reported by the subject that occur after enrollment through the end of study visit are reported using the Events CRF.

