8.2.5.1.2 Serious Adverse Events

The investigator is responsible for ensuring that all **serious adverse events** observed by the investigator or reported by the subject that occur from signing of the informed consent through the end of study visit are reported using the Event**s** CRF.

All **serious adverse events** will be collected, recorded and reported to the sponsor or designee within 24 hours of the investigator's **awareness** of the event, as indicated in Section 11.4. The investigator will submit any updated **serious adverse event** data to the sponsor within 24 hours of it being available.

Since the criteria for grade 4 in the CTCAE grading scale differs from the regulatory criteria for serious adverse events, if adverse events correspond to grade 4 CTCAE toxicity grading scale criteria (eg, laboratory abnormality reported as grade 4 without manifestation of life-threatening status), it will be left to the investigator's judgment to also report these grade 4 abnormalities as serious adverse events. For any adverse event that applies to this situation, comprehensive documentation of the event's severity must be recorded in the subject medical records.

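### The protocol gives conflicting start points for recording non-serious adverse device effects, so reactions during the screening wear test may lose their device attribution

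*Protocol*

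**What the plan says.** Five places in the protocol bear on when a device effect is recorded.

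- **Table 1-2, protocol-specified procedures.** The row "Adverse device effects" runs continuously from screening to end of study. The adverse event row above it starts at cycle 1 day 1.
- **Section 8.2.5.7.** Device effects are reported as adverse events, "following the same reporting periods and procedures".
- **Section 8.2.5.1.1.** The adverse events to report are those "that occur after enrollment through the end of study visit are reported using the Events CRF".
- **Section 8.2.5.1.2.** Serious events are those that "occur from signing of the informed consent through the end of study visit".
- **Section 8.2.1.3.** The rule for non-serious adverse events is that those "observed between the signing of the Informed Consent Form to enrolment/pre-dose cycle 1 day 1 should be captured as Medical History". No exception is made for device effects.

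The digital health rows of Table 1-2 schedule a home trial of the monitoring system (CWHMS) in screening, lasting "24-48 hours to determine eligibility". Section 9.4.2.3.2 plans a table of device-related events by system organ class and preferred term, where applicable, and states no time window for it.

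**The concern.** The screening wear test is the subject's first exposure to the devices, and Table 1-1 (panel 1) names comfort as one of its purposes. A skin reaction or similar minor effect during the test is the kind of event that the device-related row is there to capture. A site working from Table 1-2 would enter it on the Events CRF and judge its relationship to the device. A site working from Sections 8.2.5.7 and 8.2.1.3 would enter it as medical history, where the protocol describes a toxicity grade for unresolved conditions but no device attribution.

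The same reaction could then appear in the device-related event table for one site and not for another. The study is presented as one of safety and feasibility of outpatient treatment under this monitoring, so the handling of device effects should not depend on which section a site happens to follow.

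**Working it through.** There is no planned figure to reproduce. The check is whether the wear test falls inside each recording window.

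**Step 1: place the wear test.** Table 1-2 puts it in screening and uses it to decide eligibility. Section 5.3 treats a subject as enrolled once the investigator decides that all eligibility criteria are met. The wear test therefore precedes enrollment, and so also precedes cycle 1 day 1, whichever screening day it is done.

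**Step 2: apply each instruction to a device reaction in the test.**

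| Instruction | Window starts | Reaction in the wear test |
|---|---|---|
| Table 1-2, device-effect row | Screening | Collected as a device effect |
| 8.2.5.7 with 8.2.5.1.1 (non-serious) | After enrollment | Outside the window |
| 8.2.5.7 with Table 1-2, adverse event row (non-serious) | Cycle 1 day 1 | Outside the window |
| 8.2.1.3 (non-serious) | Consent, up to enrollment or pre-dose cycle 1 day 1 | Sent to medical history |
| 8.2.5.7 with 8.2.5.1.2 (serious) | Consent | Collected |

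The conflict is confined to non-serious effects. For these, the first row contradicts the next three. It does not matter which of the two adverse event start points is used.

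**Step 3: see what each route records.** Section 11.4 makes two attributes mandatory on the Events CRF: whether the event began before first dose, and its relatedness to blinatumomab, other required therapies or the CWHMS. That form can already hold a pre-dose, device-related event. Section 8.2.1.3 describes no equivalent device field for medical history.

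**Step 4: see whether the SAP settles it.** It does not. SAP Section 5 starts treatment-emergent events at first dose, so a screening event is outside those tables. SAP Section 9.6.2 lists no device-event table, and SAP Section 10 does not record that as a change from the protocol.

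**The case against.** The strongest reply is that other text already points sites to the right form. Section 8.2.5.7 itself makes the investigator responsible for documenting device effects arising in the study, and has device-related complaints and adverse events entered in the trial database. Section 11.4 sends adverse events resulting from device effects to the Events CRF. Section 8 makes adherence to the Schedule of Activities a requirement, which favours Table 1-2. Even under the other reading the reaction is still written down as medical history. For subjects who fail screening, Section 5.4 collects screen-failure details and eligibility criteria, and it recognises inability to wear the device as a reason for failure. Device tolerability is not a listed objective or endpoint, and the device-event table is conditional.

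Most of this stands as a limit on the consequence. It does not remove the conflict. None of these passages gives a start point for device effects, and none overrides the rule in Section 8.2.1.3. Section 5.4 names only serious events among the safety data for screen failures, so a minor reaction there may show only indirectly.

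A reader might infer that the screening device data are lost and cannot be recovered at analysis. The documents do not support that. Serious effects are captured from consent, medical history keeps the event, and screen-failure details are partly collected. What is at risk is the attribution to the device and consistent counting.

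**Conclusion.** The contradiction is real and minor. For non-serious device effects in the wear test, the protocol gives two incompatible recording instructions. The likely consequence is missing device attribution and uneven counting across sites in the device-related event table. This assumes that some sites would follow Sections 8.2.5.7 and 8.2.1.3 as written rather than Table 1-2. The primary endpoint and the time-to-intervention endpoint are confined to the mandatory monitoring period in cycles 1 and 2, so neither is affected, and nor is the sample size.

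The number of events involved cannot be stated, because the documents give no device-effect rate. A reader might turn to wear time. Screening wear is 24/(24 + 72 + 48) = 24/144 = 16.7% to 48/(48 + 72 + 48) = 48/168 = 28.6% of planned wear for a subject who completes both monitoring periods. That is a share of hours, not of events. It also assumes uninterrupted wear, although Section 8.2.2.1 allows removal for up to one hour a day after the first 24 hours. It should not be read as the proportion of device effects missed.

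**What to change.** Amend Section 8.2.5.7 to say that adverse device effects are recorded on the Events CRF, with relatedness to the CWHMS, from first device wear in screening, as Table 1-2 already indicates. Add to Section 8.2.1.3 that device effects are exempt from the medical-history rule. If recording is meant to include subjects who then fail screening, Section 5.4 needs a matching line. The Events CRF already has the needed fields, so the cost is a few sentences, a CRF completion note and some additional event records.

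Reporting the wear test as a separate table is optional and costs more. It would need a new SAP table and a denominator of all subjects who wore the device. No current analysis set provides that: the SAP's Full Analysis Set is enrolled subjects and its Safety Analysis Set is dosed subjects.

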8.2.6 Clinical Laboratory Assessments

Refer to Section 11.2 for the list of clinical laboratory tests to be performed and to the Schedule of Activities (Table 1-2) for the timing and frequency.

The investigator is responsible for reviewing laboratory test results and recording any clinically relevant changes occurring during the study in the Events CRF. The investigator must determine whether an abnormal value in an individual study subject represents a clinically significant change from the subject's baseline values. In general, abnormal laboratory findings without clinical significance (based on the investigator's judgment) are not to be recorded as adverse events. However, laboratory value changes that require treatment or adjustment in current therapy are considered adverse events. Where applicable, clinical sequelae (not the laboratory abnormality) are to be recorded as the adverse event.

All protocol-required laboratory assessments, as defined in Section 11.2, must be conducted in accordance with the Schedule of Activities (Table 1-2).

Date: 21 April 2022 Page 64 of 108

8.2.6.1 Pregnancy Testing

A highly sensitive (urine or serum) pregnancy test should be completed at screening and within 7 days of initiation of investigational product for females of childbearing potential.

Note: Females who have undergone a bilateral tubal ligation/occlusion should have pregnancy testing per protocol requirements. (If a female subject, or the partner of a male subject, becomes pregnant it must be reported on the Pregnancy Notification Form, see Figure 11-2). Refer to Section 11.5 for contraceptive requirements.

Additional on-treatment pregnancy testing may be performed at the investigator's discretion or as required per local laws and regulations.

8.2.7 Patient Reported Outcomes

Patient reported outcomes will be assessed with the **EORTC** QLQ-C30, which is a commonly used instrument and validated for cancer patients **across tumor types**. The instrument is scored using guidelines recommended by the EORTC. The QLQ-C30 contains an overall global health status (GHS)/quality of life (QoL) **scale**, 5 functional domains (physical, emotional, cognitive, social, and role functioning), and 9 symptom **scales** (fatigue, nausea and vomiting, pain, dyspnea, insomnia, appetite loss, constipation, diarrhea, and financial difficulties). Each domain/**scale** is scored from zero to 100; higher scores indicate better QoL, better functioning, or more severe symptoms, respectively.

8.2.8 Medical Resource Utilization

Medical resource utilization data, associated with medical encounters, will be collected in the CRF by the investigator and study-site personnel for all subjects throughout the study. Protocol-mandated procedures, tests, and encounters are excluded.

The data collected may be used to conduct exploratory economic analyses and will include:

- Number of medical care encounters, including surgeries, and other selected procedures (inpatient and outpatient)
- Use of concomitant medications associated with treatment-related AEs

Date: 21 April 2022 Page 65 of 108

9. Statistical Considerations

9.1 Statistical Hypotheses

No formal hypotheses will be tested. For the primary and secondary objectives, analyses will be descriptive and include estimations.

9.2 Sample Size Determination

The planned enrollment for this study is **approximately** 45 **patients**. The sample size is based on feasibility rather than on statistical considerations. Given a true probability of a primary endpoint event of 38%, the expected 95% upper confidence limit with 45 subjects would be 53.5%. The 38% probability is based **on** the SAE rate in first 3 days of cycle 1 and first 2 days of cycle 2 from the previous MRD study (BLAST). Based on these assumptions, we expect to observe approximately 17 subjects who will experience the primary endpoint which should provide an initial indication of the timeliness of the therapeutic intervention when outpatient blinatumomab in administered in conjunction with remote digital monitoring.

9.3 Analysis Sets, Subgroups, and Covariates

9.3.1 Analysis Sets

Safety Analysis Set (SAS)

All enrolled subjects who receive at least 1 dose of blinatumomab. The analysis of secondary safety and resource utilization endpoints will be conducted on the SAS.

Primary Analysis Set (PAS)

All subjects in the SAS who were not replaced (see Section 4.2.1). The analysis of primary and key secondary endpoint will be conduct on the PAS.

Patient Reported Outcomes Analysis Set

The Patient Reported Outcomes (PRO) Analysis Set will include all subjects in the SAS with a non-missing baseline and at least 1 non-missing post-baseline result for EORTC QLQ-C30. Subjects will be included in the analysis of each EORTC QLQ-C30 for which they have non-missing data.

9.3.2 Covariates

The relationship between covariates and safety endpoints may be explored if appropriate.

Date: 21 April 2022 Page 66 of 108

9.3.3 Subgroups

The subgroup analysis may be performed but could be limited by the small sample size of the study.

9.3.4 Handling of Missing and Incomplete Data Subjects will be replaced for analysis if the outpatient monitoring during blinatumomab infusion is not established.

Subjects are removed from IP due to disease progression.

Replacement status is only applicable for internal data analysis.

Details on handling of missing and incomplete data are described in the statistical analysis plan.

